1. ABBREVIATIONS

AMM: Marketing Authorization

ANSM: French National Agency for the Safety of Medicines and Health Products

ARC: Clinical Research Associate

BPC: Good Clinical Practices

BPF: Good Manufacturing Practices

CEC: Cardiopulmonary Bypass

CMC: Medical-Surgical Center

CNIL: French National Commission for Information Technology and Civil Liberties

CPP: Committee for the Protection of Persons

DFG: Glomerular Filtration Rate

DSUR: Development Safety Update Report

ECG: Electrocardiogram

EI: Adverse Event

EIG: Serious Adverse Event

EMA: European Medicines Agency

EVA: Visual Analog Scale

FC: Heart Rate

IDE: Registered Nurse

IV: Intravenous

MDRD: Modification of Diet in Renal Disease

mITT: Modified Intention to Treat

MR: Reference Methodology

NVPO: Postoperative Nausea and Vomiting

PAS: Systolic Blood Pressure

RCP: Summary of Product Characteristics

SNC: Central Nervous System

SpO2: Pulse Oxygen Saturation

SUSAR: Suspected Unexpected Serious Adverse Reaction

TA: Blood Pressure

UEM: Morphine Equivalent Units

USC: Continuous Care Unit

2. SCIENTIFIC JUSTIFICATION AND GENERAL DESCRIPTION

2.1. Study Context

Digestive complications following cardiac surgery are frequent and worsen patient prognosis. Paralytic ileus and Ogilvie syndrome are among these complications. They represent a real management challenge in intensive care, inducing morbidity-mortality, extended hospital stays, and significant postoperative costs. Few treatments appear effective for bowel transit recovery other than neostigmine, which has non-negligible side effects, particularly cardiac.

After cardiac surgery, opioid analgesics are frequently used to relieve pain, particularly sternotomy pain. Through their pharmacological effect, they contribute to postoperative paralytic ileus. Opioid receptors are distributed throughout the central nervous system, where they are involved in pain perception, but also peripherally, including in the mesenteric nervous system where they regulate peristalsis. Opioid receptor antagonists are therefore a prime target.

Naloxegol is a peripherally acting opioid receptor antagonist in tablet form, from the alvimopan family. It was designed to antagonize peripheral, but not central, effects of opioids at therapeutic doses. It is a substrate of cytochrome P450 and CYP3A4, rapidly absorbed with a mean time to maximum plasma concentration of 2 hours. Following once-daily administration, steady-state plasma concentrations are reached within 2-3 days with minimal accumulation. The main elimination route is hepatic, with minimal renal excretion.

Research hypothesis: Adding naloxegol pre- and postoperatively in cardiac surgery could reduce the time to bowel transit recovery and the rate of digestive and respiratory complications, as well as the duration of intensive care stay, without negative effects on analgesia.

2.2. Research Objective

The objective of this study is to demonstrate that the administration of naloxegol in the perioperative period of cardiac surgery reduces the duration of postoperative ileus.

2.3. Summary of Benefits and Foreseeable Risks

2.3.1. Expected Benefits for the Patient

Expected benefits include a reduction in the rate of digestive complications, discomfort, pneumonia rate, and duration of hospitalization.

2.3.2. Foreseeable and Known Risks

The main risks associated with this clinical trial are related to the administration of naloxegol. In pooled clinical trial data, the most frequently reported adverse effects with naloxegol ($\geq 5\%$) are: abdominal pain, diarrhea, nausea, headache, and flatulence. The majority of gastrointestinal adverse effects were evaluated as mild to moderate, occurred at the start of treatment, and resolved upon continuation.

2.4. Description of the Study Population

Adult patients scheduled for cardiac surgery under cardiopulmonary bypass (CPB).

3. RESEARCH OBJECTIVES

3.1. Primary Objective

To evaluate the effect of perioperative naloxegol administration in cardiac surgery on the duration of postoperative ileus.

3.2. Secondary Objectives

- Evaluate the effect of naloxegol on digestive complications
- Evaluate the effect of naloxegol on respiratory complications
- Evaluate the rate of infectious complications
- Verify the maintenance of normal analgesia
- Compare total hospitalization durations
- Compare lengths of stay in intensive care unit and continuous care unit (CCU)

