4.2. Secondary Endpoints

Related to Secondary Objective 1 – Digestive Complications Rate:

- Intra-abdominal pressure measured via an adapted urinary catheter on Day 1 and Day 2 minimum, until measurement is feasible (cmH₂O)
- Vomiting
- Ogilvie syndrome defined by an occlusive syndrome >72h and cecal distension >8cm
- Mesenteric ischemia documented via abdominal imaging, colonoscopy, or laparoscopy
- Need for colonoscopy
- Placement of nasogastric tube
- Intolerance to solid food at Day 2

Related to Secondary Objective 2 – Respiratory Complications Rate:

- Duration (hours) of invasive and non-invasive mechanical ventilation (NIV, Optiflow)
- Reintubation
- Assisted ventilation (invasive or non-invasive) at Day 2
- Pneumonia, defined by a radiological infiltrate plus at least 2 criteria: T>38°C; leukocytosis or leukopenia; purulent secretions

Related to Secondary Objective 3 – Infectious Complications Rate:

- Septicemia defined by two positive blood cultures with the same organism within 48h (catheter or peripheral)
- Superficial or deep sternal infection (return to operating room for wound)

Related to Secondary Objective 4 – Pain Assessment:

- VAS (Visual Analog Scale) at Day 1, Day 2, and Day 3
- Total opioid consumption in morphine equivalent mg

Related to Secondary Objective 5:

- Total hospitalization duration in days

Related to Secondary Objective 6:

- Length of stay in intensive care unit and CCU in days

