9. STATISTICS

9.1. Statistical Methods

The analysis will proceed in 3 stages:

Descriptive Analysis:

Description of the total population and by group. For categorical variables: absolute and relative frequencies. For normally distributed continuous variables: mean and standard deviation. For non-normal distributions: median and interquartile range.

Inferential Analysis:

Comparisons between the 2 randomized groups will use chi-squared test for categorical variables; Student's t-test for Gaussian continuous variables; Wilcoxon-Mann-Whitney test for non-Gaussian variables. For pain scores over time, a mixed model for repeated measures will be used.

Exploratory Analysis:

Bivariate (correlation coefficients) or multivariate tests (multiple regression, logistic regression) to determine relationships between variables, including the effect of age, sex, and obesity (BMI>30).

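### The analgesia objective is a no-worsening claim, but the plan sets no margin or confidence-interval criterion for it and no time window for total opioid use

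*Combined protocol and SAP*

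**What the plan says.** Of the six secondary objectives in section 3.2, five are worded as evaluations or comparisons. The analgesia objective is different: "Verify the maintenance of normal analgesia". Section 2.1 makes the same idea part of the research hypothesis, in which the hoped-for benefits are to come "without negative effects on analgesia".

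Section 4.2 gives two endpoints for this objective: "VAS (Visual Analog Scale) at Day 1, Day 2, and Day 3" and "Total opioid consumption in morphine equivalent mg". The first is tied to fixed days. The second has no start, no end and no per-day basis.

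For analysis, section 9.1 states: "For pain scores over time, a mixed model for repeated measures will be used". Other continuous variables, including the opioid total, are compared by t-test or Wilcoxon-Mann-Whitney test. Section 9.3 sets a two-sided 0.05 threshold. No section gives a non-inferiority or equivalence margin, a confidence-interval rule, or any other criterion for calling analgesia maintained.

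The plan expects shorter stays on naloxegol. The section 2.1 hypothesis includes a reduction in complications "as well as the duration of intensive care stay", and the reductions expected in section 2.3.1 include "discomfort, pneumonia rate, and duration of hospitalization". Stay is itself an endpoint: "Compare total hospitalization durations".

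**The concern.** A difference test asks whether the data contradict equality. It does not ask whether a worsening large enough to matter has been ruled out. For an opioid antagonist the second question is the relevant one, and the objective is worded as if the trial will answer it. Without a margin, a p-value above 0.05 is compatible both with no effect on pain and with a worsening that the trial could not detect.

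The two analgesia endpoints also have to be read together, because similar pain scores can be obtained with more opioid. That needs opioid use to be counted over the same period as the scores. With the window open, the total could be taken over the stay, over the ICU period or over some number of days, and the choice could be made after the data are seen. If it is taken over the stay, a treatment that shortens stay lowers the total without any change in daily use.

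At stake is one stated part of the hypothesis. The primary endpoint and its sample size are not affected.

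**Working it through.** **The plan's own figure.** None is given for analgesia. The 150 per group used below comes from section 9.2, where it was derived for time to bowel transit recovery.

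**Objective against analysis.**
- Claim required: naloxegol does not worsen analgesia (sections 2.1 and 3.2).
- Tools provided: difference tests and a mixed model at two-sided 0.05 (sections 9.1 and 9.3).
- Missing link: a margin, and a rule comparing a confidence limit with it.

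**Precision for VAS.** The documents give neither the scale range nor an SD. Assume a 0–10 scale and SDs of 1.5, 2 and 2.5, at a single time point.

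SE = SD × √(2/150) = SD × 0.1155. The 95% half-width is 1.96 × SE. Power to exclude a worsening of M when the true difference is zero is Φ(M/SE − 1.96), with M = 1 as an illustration. The chance that a true worsening of 0.5 gives p > 0.05 is 1 − Φ(0.5/SE − 1.96).

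| SD | SE | 95% half-width | Power to exclude 1 point | True 0.5 worsening gives p > 0.05 |
|---|---|---|---|---|
| 1.5 | 0.173 | 0.34 | >99% | 18% |
| 2 | 0.231 | 0.45 | 99% | 42% |
| 2.5 | 0.289 | 0.57 | 93% | 59% |

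**Three-day mean.** The planned model covers Days 1–3. With equal variances and between-day correlation ρ, the SE of the mean difference is multiplied by √((1 + 2ρ)/3). At SD 2:

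| Assumed ρ | SE | 95% half-width | True 0.5 worsening gives p > 0.05 |
|---|---|---|---|
| 0.3 | 0.169 | 0.33 | 16% |
| 0.5 | 0.189 | 0.37 | 24% |
| 0.7 | 0.207 | 0.40 | 32% |

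The single-time-point figures are therefore the pessimistic end for the three-day estimate.

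**What a 1-point margin would and would not do.** At SD 2 and one time point, a true 0.5-point worsening would still satisfy a 1-point margin with probability Φ((1 − 0.5)/0.231 − 1.96) = 58%. The miss rate for 0.5 point is thus no argument for a 1-point margin. The margin has to be chosen on clinical grounds.

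**Opioid total, if counted over the stay.** With constant daily use, total = daily use × days. If stay falls by a fraction r and daily use rises by g, the total is unchanged when (1 + g)(1 − r) = 1, so g = 1/(1 − r) − 1.

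| Stay shorter by | Daily use higher by, with no change in total |
|---|---|
| 5% | 5.3% |
| 10% | 11.1% |
| 15% | 17.6% |
| 20% | 25.0% |

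The documents give no expected size for the reduction in stay, so these rows are a range and not a forecast.

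**The case against.** The strongest reply is that the plan nowhere says a p-value above 0.05 will be taken as proof of maintained analgesia. Section 9.1 also plans description by group, and the mixed model will naturally yield an estimate and an interval. This is correct. A reader might infer that the sponsor intends to read non-significance as preservation, but the documents contain no such rule. What stands is that they contain no other rule either, so the conclusion named in the objective has no defined route from the data.

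Second, a reader might infer that the opioid total runs over an unequal stay and is therefore biased in favour of naloxegol. Section 4.2 does not say so. Accumulation over the stay is one plausible reading of an undefined window, and the bias is conditional on it. Constant opioid use throughout the stay is a further assumption. The stay problem does not touch VAS, which is taken on fixed days. Deaths add little to it as an argument, because section 9.7 already excludes early deaths without transit recovery.

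Third, a large worsening would seldom escape the existing test: a true 1-point worsening would give p > 0.05 only about 1% of the time at SD 2 and 7% at SD 2.5. That is fair, and it limits the practical harm. But it depends on an SD that the plan does not state, and it still leaves the reader to choose after the fact which worsening matters.

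Finally, section 2.1 describes naloxegol as designed to spare central opioid effects, and analgesia is only one of several parts of the hypothesis. The first is a reason to expect maintenance, not evidence of it. The second bears on the weight of the point, not on its validity.

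**Conclusion.** The point holds in this form: the plan states a no-worsening objective for analgesia without a margin or confidence-interval criterion, and leaves the opioid window undefined. Followed as written, it could report that no difference was found but could not support a statement that analgesia was maintained.

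The omission is avoidable at the planned size: under the assumed SDs of 2 to 2.5, a 1-point worsening could be excluded with 99% to 93% power at one time point if there is no true difference, and precision improves over three days. These figures rest on an assumed SD and scale and on an illustrative margin.

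The documents do not support saying that the opioid comparison is biased. They support saying that it could be, by an amount such as 11% in daily use for a 10% shorter stay, if the total is taken over the stay.

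**What to change.** 1. From the planned mixed model, estimate the naloxegol minus placebo difference in mean VAS over Days 1–3 with its two-sided 95% confidence interval.
2. Claim maintenance only if the upper limit lies below a margin that the sponsor justifies and fixes before unblinding. The 1 point used above is only an illustration.
3. If no margin is set, call the analysis descriptive, reword the objective in section 3.2 accordingly, and make no claim of maintenance.
4. Define opioid consumption over one window common to all patients and matched to the VAS days, for example end of surgery to 72 h. Report the between-arm difference with its 95% confidence interval beside the VAS result.

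The cost is mainly SAP wording and the work of justifying a margin. No extra patients are needed. Two downsides should be accepted openly. The trial may have to report that maintenance was not shown. Opioid doses must also be recorded so that they can be attributed to the window. Section 13.1 does not say whether the eCRF captures dated doses or a single total; if it is a single total, data collection has to change as well.

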4. JUDGMENT CRITERIA

4.1. Primary Endpoint

Time (in hours) to bowel transit recovery after cardiac surgery, defined as the duration in hours between the first anesthetic induction and the emission of the first significant stool (approximately 100g as judged by the nursing assistant or nurse in charge of the patient, blinded to treatment).

The number of patients who received macrogol and the number who received picosulfate will be indicated for each arm.

4.2. Secondary Endpoints

Related to Secondary Objective 1 – Digestive Complications Rate:

- Intra-abdominal pressure measured via an adapted urinary catheter on Day 1 and Day 2 minimum, until measurement is feasible (cmH₂O)
- Vomiting
- Ogilvie syndrome defined by an occlusive syndrome >72h and cecal distension >8cm
- Mesenteric ischemia documented via abdominal imaging, colonoscopy, or laparoscopy
- Need for colonoscopy
- Placement of nasogastric tube
- Intolerance to solid food at Day 2

Related to Secondary Objective 2 – Respiratory Complications Rate:

- Duration (hours) of invasive and non-invasive mechanical ventilation (NIV, Optiflow)
- Reintubation
- Assisted ventilation (invasive or non-invasive) at Day 2
- Pneumonia, defined by a radiological infiltrate plus at least 2 criteria: T>38°C; leukocytosis or leukopenia; purulent secretions

Related to Secondary Objective 3 – Infectious Complications Rate:

- Septicemia defined by two positive blood cultures with the same organism within 48h (catheter or peripheral)
- Superficial or deep sternal infection (return to operating room for wound)

Related to Secondary Objective 4 – Pain Assessment:

- VAS (Visual Analog Scale) at Day 1, Day 2, and Day 3
- Total opioid consumption in morphine equivalent mg

Related to Secondary Objective 5:

- Total hospitalization duration in days

Related to Secondary Objective 6:

- Length of stay in intensive care unit and CCU in days

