9.2. Sample Size Calculation

Primary endpoint: time to bowel transit recovery (quantitative variable). Calculation based on a mean transit recovery time of 48 hours postoperatively. For a 15% reduction (48h to 41h) in the treated group, standard deviation of 20h, alpha risk of 5%, power of 80%, bilateral test: 300 inclusions needed (150 patients per group).

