9.3. Significance Level

Bilateral threshold: 0.05

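### The pneumonia endpoint does not require a new infiltrate or signs that occur together, so some non-pneumonia cases can be counted after bypass

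*Combined protocol and SAP*

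**What the plan says.** Section 4.2 (Secondary Endpoints) lists pneumonia under the respiratory objective: "Pneumonia, defined by a radiological infiltrate plus at least 2 criteria: T>38°C; leukocytosis or leukopenia; purulent secretions". It names no reference film, no period within which the signs must coincide and no white-cell limits. No other section supplies them. Section 6.2.4 provides for daily collection of vital status and adverse events in hospital and a telephone call at 1 month. Section 9.1 says only that "Comparisons between the 2 randomized groups will use chi-squared test for categorical variables", and section 9.3 sets "Bilateral threshold: 0.05". No adjudication of pneumonia is described.

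Neighbouring items in section 4.2 are tighter. One reads "Septicemia defined by two positive blood cultures with the same organism within 48h (catheter or peripheral"; another is fixed in time, "Assisted ventilation (invasive or non-invasive) at Day 2". Pneumonia also carries some weight in the rationale. Section 2.3.1 states: "Expected benefits include a reduction in the rate of digestive complications, discomfort, pneumonia rate, and duration of hospitalization".

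**The concern.** Two of the three accompanying signs, fever and an abnormal white count, are general signs of inflammation that major surgery can itself produce, and every participant has cardiac surgery under bypass. Those two signs plus any infiltrate meet the rule, so no respiratory sign is needed. Because newness and coincidence are not required, the infiltrate could also predate surgery, or the fever could come from another source such as a sternal infection, which is a separate endpoint under the infectious objective.

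Two things are at stake. The reported pneumonia rate may be too high, and a real effect on a named expected benefit may look smaller than it is. Separately, and whatever the false-positive rate, two assessors could classify the same patient differently because the reference film, the window and the white-cell limits are left open.

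**Working it through.** **1. The plan's own figures.** There is no rate, effect size or power for pneumonia to reproduce. The only figure borrowed here is 150 patients per group from section 9.2, which was set for the primary endpoint. Its stated inputs (7h difference, SD 20h, two-sided 5%, 80% power) give 2 × (1.960 + 0.842)² × 20² / 7² = 128.1, so 129 per group. The stated 150 is larger than that, and the difference has no bearing on this point.

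**2. What the rule requires, beside its neighbours in section 4.2.**

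| Endpoint | Limit on time or coincidence | Other limit |
|---|---|---|
| Septicemia | two cultures within 48h | same organism |
| Ogilvie syndrome | more than 72h | cecum over 8cm |
| Assisted ventilation | Day 2 | none |
| Pneumonia | none | temperature above 38°C; white-cell limits not given |

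Two of three signs can be met by fever + white count, fever + secretions, or white count + secretions. The first pair contains nothing respiratory.

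**3. Effect of false positives.** Let p be the true risk in an arm and f the share of patients without pneumonia who still meet the rule, equal in both arms. Then:

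- observed risk = p + (1 − p) × f
- observed difference = (p_control − p_naloxegol) × (1 − f)

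The ratio of observed risks moves towards 1 for any f above 0.

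**4. Assumed inputs (none is in the documents).** True risk 8% vs 4%. Opacity read as an infiltrate on early films 10–30%, temperature above 38°C 30–50%, abnormal white count 50–80%, taken as independent. Then f runs from 0.10 × 0.30 × 0.50 = 0.015 to 0.30 × 0.50 × 0.80 = 0.12.

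Power uses the Normal approximation with n = 150 per arm: Φ(d / SE − 1.96), where d is the observed difference and SE = √[(p1(1 − p1) + p2(1 − p2)) / 150]. For f = 0: SE = √[(0.0736 + 0.0384) / 150] = 0.0273, and Φ(0.04 / 0.0273 − 1.96) = 31%.

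| f | Control | Naloxegol | Risk ratio | Difference | Power |
|---|---|---|---|---|---|
| 0 | 8.00% | 4.00% | 0.50 | 4.00 points | 31% |
| 1.5% | 9.38% | 5.44% | 0.58 | 3.94 points | 26% |
| 4% | 11.68% | 7.84% | 0.67 | 3.84 points | 20% |
| 8% | 15.36% | 11.68% | 0.76 | 3.68 points | 15% |
| 12% | 19.04% | 15.52% | 0.82 | 3.52 points | 12% |

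The bias falls mainly on the ratio and on the reported rates. The absolute difference shrinks only by the factor 1 − f.

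**5. Dependence on the assumed rate.** With a true ratio of 0.50 and f = 5%, a true control risk of 5%, 10% or 15% gives an observed ratio of 0.76, 0.67 or 0.63. The direction is the same; the size is not fixed.

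**6. Would a stricter rule do better?** Suppose onset at least 48h after surgery and persistence on the next film were also required. Assume that this removed every false positive but lost 20% or 25% of true cases. The risks become 6.4% vs 3.2% or 6.0% vs 3.0%. The ratio stays at 0.50, and power is 25.5% or 24.1%. The present rule at f = 1.5% has 25.7%, so at the low end of the range the stricter rule gains no power. At f = 12% it would.

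**The case against.** The strongest counter-argument is that the size is unknown. A reader might infer that ordinary inflammation and atelectasis do score as pneumonia in this trial and dilute the effect by a known amount. The documents do not support that. They give no frequency of pneumonia, fever, abnormal white count or infiltrate, and the assumed f spans an eightfold range, with little change in the ratio at its low end. The rule speaks of an infiltrate and does not mention atelectasis, so an assessor would have to read one as the other. Counting an unchanged preoperative opacity, or joining an early film to a much later fever, takes a literal reading against the evident purpose of the endpoint. All of this stands, and it limits the point to what the rule permits.

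A reader might also infer that onset at least 48h after surgery has to be part of the definition. That is a trade-off, as step 6 shows. It could also remove relevant cases: dosing starts two hours before surgery, vomiting is a listed endpoint, and the reference list includes a study whose title links enteral naloxone to less gastric reflux and pneumonia.

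Finally, pneumonia is one of many secondary measures and is underpowered on the assumed rates even with a perfect definition. With false positives equal in both arms, the bias is towards no effect and does not manufacture a benefit. That limits the weight of the point. It does not remove the gap, because secondary endpoints are reported as estimates and rates.

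**Conclusion.** The point holds as a cheap improvement to an endpoint definition. The rule as written can count patients without pneumonia, because it requires neither a new infiltrate nor signs that occur together. The bias towards a ratio of 1 follows arithmetically if false positives are equally frequent in both arms, which is what effective double-blinding would lead one to expect. If blinding failed, or if the share of false positives differed between arms for another reason, the bias could go either way.

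The size is illustrative only: from 0.50 to between 0.58 and 0.82 for an assumed 8% vs 4% and f of 1.5% to 12%. The primary endpoint, the sample size and the main conclusion of the trial are not affected.

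**What to change.** Before unblinding, amend section 4.2 so that the event is a new or progressive infiltrate compared with the preoperative film, plus at least two of the three listed signs within the same 48h of that film. State the numerical limits for leukocytosis and leukopenia. Record in the eCRF the date of the film and the onset date of each sign.

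Leave onset at least 48h after surgery, and persistence on a next film, out of the main definition. Report two sensitivity analyses: one restricted to onset from 48h after surgery, and one using the present rule.

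The cost is protocol wording and slightly more data entry. A few genuine cases whose signs do not coincide would be counted only in the sensitivity analysis under the present rule. A change made after unblinding would look data-driven, so the timing matters more than the effort.

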6.2. Study Conduct

6.2.1. In the Cardiology/Cardiac Surgery Ward:

a) Inclusion: Patients will be informed of the protocol by an investigator physician during the cardiology consultation. Clear and transparent information will be provided orally and in writing. Inclusion and non-inclusion criteria will be verified. Informed consent will be obtained after a reflection period deemed sufficient by the patient.

b) Randomization: Patients will be randomized the day before surgery (1:1) into two groups:

- Naloxegol Group: Interventional arm receiving the experimental treatment 'naloxegol'
- Placebo Group: Comparison arm receiving an inert tablet

Randomization will be performed electronically via the eCRF by a nurse 'outside the protocol' who will administer the treatment according to the randomization group.

6.2.2. In the Operating Room:

Standard management of patients for anesthesia and cardiac surgery.

6.2.3. In the ICU and CCU:

- Standard patient management
- Naloxegol Group: administration of a naloxegol 25mg tablet at 24h postoperatively, then every 24h until bowel transit recovery, maximum 5 days
- Placebo Group: administration of an inert tablet at 24h postoperatively, then every 24h until bowel transit recovery, maximum 5 days
- At Day 2 in absence of bowel transit: administration of macrogol until transit recovery
- At Day 4 in absence of bowel transit: administration of sodium picosulfate (Citrifleet)

6.2.4. In the Ward and at Home:

Collection of patient vital status and possible adverse events daily during hospitalization, then at 1 month by telephone call.

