6.8. Stopping Rules for Individual Participants

Any subject included in the study may withdraw consent at any time for any reason without explanation and without affecting the care provided. Early death without bowel transit recovery (absence of primary endpoint) will lead to exclusion from analysis (mITT). These patients will be replaced to avoid loss of statistical power.

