9.7. Analysis Population

Modified intention-to-treat (mITT) population: all randomized patients excluding those who died early without bowel transit recovery (absence of primary endpoint). Each patient will be analyzed in their randomization group. A CONSORT diagram will be provided.

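### Ventilation time and lengths of stay have no rule for deaths after transit recovery, so a death is scored by when it occurs

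*Combined protocol and SAP*

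**What the plan says.** Section 4.2 lists three durations among the secondary endpoints. Under respiratory complications it has "Duration (hours) of invasive and non-invasive mechanical ventilation (NIV, Optiflow"; under objective 5, "Total hospitalization duration in days"; under objective 6, "Length of stay in intensive care unit and CCU in days". None carries a rule for a patient who dies.

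Section 9.1 assigns the tests by distribution: "Student's t-test for Gaussian continuous variables; Wilcoxon-Mann-Whitney test for non-Gaussian variables". It names no competing-risk, worst-rank or free-days method.

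Deaths are addressed in two places only. Section 6.8 states: "Early death without bowel transit recovery (absence of primary endpoint) will lead to exclusion from analysis (mITT"; it adds that such patients are replaced. Section 9.7 defines the analysis set as "all randomized patients excluding those who died early without bowel transit recovery (absence of primary endpoint". Neither section says how early a death must be, and neither covers a death after recovery.

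The data needed for a rule are planned. Section 6.2.4 provides for "Collection of patient vital status and possible adverse events daily during hospitalization, then at 1 month by telephone call". Mortality itself is not a listed endpoint.

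**The concern.** Death ends a hospital stay and a period of ventilation. If the observed length goes into the test as it stands, a patient who dies on day 3 in the ICU has the same value as one who leaves the ICU well on day 3. The mITT rule does not prevent this, because it acts only on deaths without transit recovery. The planning mean for recovery is 48 h (section 9.2) and follow-up runs to about one month (section 6.5), so for a typical patient most of the follow-up lies in the period without a death rule.

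This matters because the plan reads a shorter stay as benefit. The research hypothesis in section 2.1 includes it: "as well as the duration of intensive care stay, without negative effects on analgesia". With no mortality endpoint, no pre-specified comparison would warn a reader that part of a shorter mean stay came from deaths.

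**Working it through.** **The plan's own figure.** The only computed figure is the sample size for the primary endpoint. From the section 9.2 inputs (difference 7 h, SD 20 h, two-sided 5%, power 80%), n per arm = 2 × (1.96 + 0.84)² × 20² / 7² = 128, or 129 with the t correction: 258 in total, against 300 stated. The stated number is larger than the inputs require. This does not bear on the present point; only the 150 per arm is used below.

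**Upper bound on the shift.** Let pA and pB be the proportions who die in each arm. Moving every death from best to worst rank changes the Mann-Whitney probability by

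pA(1 − pB) − pB(1 − pA) = pA − pB.

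The documents give no mortality rate. Assuming a difference of 1 to 3 points, the shift is 0.01 to 0.03.

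**Yardstick.** The null standard error at 150 per arm is sqrt(301 / (12 × 150 × 150)) = 0.0334. The effect detectable with 80% power is 2.8 × 0.0334, about 0.093. The bound is therefore about 11% (0.01/0.093) to 32% (0.03/0.093) of it.

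**Why this is a ceiling.** Raw durations do not put deaths at the best rank. Assume survivors' ICU/CCU stay is lognormal with median 5 days and log-SD 0.6.

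- A death on day 3 lies at Φ(ln(3/5)/0.6) = Φ(−0.85), about the 20th percentile. Its distance from a neutral rank is 0.30, so the shift from neutral is 0.30 × (0.01 to 0.03) = 0.003 to 0.009, or 3% to 10% of 0.093. Its distance from the worst rank is 0.80, which gives 0.008 to 0.024.
- A death on day 10 lies at Φ(ln(10/5)/0.6) = Φ(1.16), about the 88th percentile. It already counts as a long stay. Its distance from the worst rank is 0.12, a shift of 0.001 to 0.004.

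**Illustrative simulation.** All inputs are assumed: 150 per arm, the same survivor distribution in both arms, 2% deaths in arm A, Wilcoxon test at two-sided 5%, 3,000 runs. The last two columns give the share of runs in which arm B was declared significantly better / worse (nominal 2.5% each).

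| Deaths in B | Day of death | Mean raw difference, B − A (days) | Raw stay | Death ranked worst |
|---|---|---|---|---|
| 2% | 2–4 | +0.01 | 3.0% / 2.3% | 2.5% / 2.4% |
| 4% | 2–4 | −0.05 | 3.2% / 1.4% | 1.3% / 4.4% |
| 6% | 2–4 | −0.11 | 5.1% / 1.0% | 0.5% / 9.4% |
| 10% | 2–4 | −0.24 | 10.2% / 0.4% | <0.1% / 21.4% |
| 4% | 10–25 | +0.23 | 1.1% / 4.7% | 1.2% / 4.9% |
| 6% | 10–25 | +0.46 | 0.7% / 8.7% | 0.5% / 8.3% |
| 10% | 10–25 | +0.93 | 0.1% / 20.0% | 0.1% / 23.0% |

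With early deaths, the raw comparison leans towards the arm with more deaths, and ranking death worst reverses the direction. With late deaths, the two analyses nearly agree. At a 2-point excess the early-death effect is barely visible: 3.2% against 3.0% with equal mortality, where the simulation error is about sqrt(0.025 × 0.975 / 3000) = 0.3 points.

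**The case against.** A reader might infer that the plan scores every death after recovery as a favourable outcome. The documents do not say so. They are silent, and the consequence follows only from applying section 9.1 to the variables in section 4.2. The direction also depends on timing: late deaths lengthen the raw stay. Since some of the earliest deaths are already removed by the mITT rule, those that remain are less likely to be the very early ones that flatter an arm. This stands.

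A reader might also take 11% to 32% of the detectable effect as the expected bias. It is a best-versus-worst ceiling on an assumed mortality difference. One to three points is 1.5 to 4.5 extra deaths per 150, in non-urgent surgery with moderate or severe renal impairment and cirrhosis excluded (sections 5.1 and 5.2). This stands too.

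Ventilation time is the weakest of the three cases. Section 4.2 counts assisted ventilation at Day 2 as a complication, so many patients who die after recovery will already have been extubated, or will have had prolonged ventilation that raises their total.

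Finally, raw stay is a legitimate measure of resource use, and comparing stays is a stated objective (section 3.2). That is a reason to keep and report it. It does not justify a test of benefit in which the score for a death depends on its date.

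**Conclusion.** The gap is real and modest. For three secondary endpoints, a death after transit recovery enters the comparison at a truncated value, which helps or harms its arm according to when it occurred. Because the sections on deaths leave early undefined, the set of deaths that enters is not fixed either.

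No trial-specific size can be computed, since the documents give neither mortality nor a distribution of stay. On an assumed 1 to 3 point mortality difference, the ceiling of 0.01 to 0.03 is approached only if nearly all the excess deaths fall very early; the effect is likely much less. The documents do not support a claim that the comparisons are biased towards the arm with more deaths as a rule, or that the primary endpoint is touched by this point. It is a cheap improvement to secondary analyses.

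**What to change.** Before unblinding, state in section 9.1 that the between-arm test for these three endpoints gives death the worst rank, and amend section 4.2 to match. One way:

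- days alive and out of hospital, and days alive and out of ICU/CCU, counted to the 1-month contact, preferably to one fixed day that the call covers for every patient;
- ventilation-free hours alive over a stated window, with its length and starting point given;
- deaths in the window scored 0, all randomised patients included, Wilcoxon test.

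The text should say whether days of readmission count, because the documents do not list readmission among the data collected. Including all randomised patients treats deaths before and after recovery alike for these endpoints.

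Keep the raw durations as descriptive resource-use results and report mortality by arm beside them.

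Vital status is already collected to 1 month, and the stay endpoints already require discharge dates, so the cost is mainly wording in two sections. The real downside is interpretive: each result becomes a composite of death and stay, on a less familiar scale than days in hospital.
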